9.3.2 Pharmacokinetic Statistical Methodology

PK parameters will be evaluated to determine the bioequivalence of ixekizumab alternate formulation (test) compared to the ixekizumab commercial formulation (reference). Log-transformed C_{\max} , $\text{AUC}(0-\infty)$ and $\text{AUC}(0-t_{\text{last}})$ will be evaluated in a linear mixed-effects model with fixed effects for formulation and a random effect for subject. The treatment differences will be back-transformed to present the ratios of geometric means and the corresponding 90% CI.

Example SAS code:

```
proc mixed data=pk;
  by parameter;
  class formulation subject;
  model log_pk= formulation / residual ddfm=kr;
  random intercept / subject=subject;
  estimate 'Test - Ref' trtmnt -1 1 / cl alpha=0.1;
run;
```

The t_{\max} will be analyzed using a Wilcoxon rank sum test. Estimates of the median difference based on the observed medians, 90% CIs and p-values from the Wilcoxon rank sum test will be calculated.

Bioequivalence will be concluded if the 90% CI is completely contained within the interval (0.80, 1.25).

PK parameters may be normalized by body weight for summarizing the data and may be summarized by site of injection location using descriptive statistics. Additional comparisons may also be conducted as necessary.

A sensitivity analysis will be performed to complete the statistical comparison above using the subjects who completed the PK sampling schedule to Day 85 only (subjects with no missing PK samples).

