5.1. Overall Design

Infection risk

Participants should follow local guidance and clinical research unit (CRU) precautions to minimize risk for COVID-19 infection.

Study RHCU is a Phase 1, subject-blind, 2-arm, randomized, parallel-design study in healthy subjects.

All subjects will be screened within 28 days prior to enrollment. Eligible subjects will be admitted to the CRU on Day -1. At screening, subjects will be stratified into 1 of 3 weight categories (<70.0 kg, 70.0 to 80.0 kg, >80.0 kg). Within the 3 weight categories, subjects will be randomized 1:1 to either 80-mg ixekizumab commercial formulation (reference) or 80-mg ixekizumab alternate formulation (test) and subrandomized 1:1:1 to injection site (arm, thigh, or abdomen) (Table RHCU.2). On Day 1, subjects will receive a single SC dose according to the randomization plan (Table RHCU.2 and Schedule of Activities, Section 2).

The desire is to have approximately equal numbers of subjects in each weight category to avoid a large difference in mean weight between the test and reference formulation groups. A subject population of 72 per weight group is an approximate target with the recommended weight categories selected based on the distribution of weights in the prior studies, RHCS and RHCT. The number of subjects assigned to each formulation and the number of subjects assigned to each site of injection location is desired to be balanced.

Table RHCU.2. Study RHCU Stratification and Randomization Plan

Weight Category (Subjects)	Formulation (80-mg ixekizumab)	Subcutaneous Injection Location ^a	Desired Number of Subjects
Low <70.0 kg (72 subjects)	Commercial (reference)	Arm	12
	Alternate (test)		12
	Commercial (reference)	Abdomen	12
	Alternate (test)		12
	Commercial (reference)	Thigh	12
	Alternate (test)		12
Medium 70.0 kg – 80.0 kg (72 subjects)	Commercial (reference)	Arm	12
	Alternate (test)		12
	Commercial (reference)	Abdomen	12
	Alternate (test)		12
	Commercial (reference)	Thigh	12
	Alternate (test)		12
High >80.0 kg (72 subjects)	Commercial (reference)	Arm	12
	Alternate (test)		12
	Commercial (reference)	Abdomen	12
	Alternate (test)		12
	Commercial (reference)	Thigh	12
	Alternate (test)		12

Abbreviations: RHCU = I1F-MC-RHCU; SC = subcutaneous.

- a A dose of investigational product will consist of 1 SC injection of 80-mg ixekizumab into the arm, thigh, or abdomen. All doses will be administered by trained site staff.

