5.2. Number of Participants

Up to approximately 240 subjects may be enrolled so that approximately 216 subjects complete the study (108 in the 80-mg ixekizumab commercial formulation [reference] group and 108 in the 80-mg ixekizumab alternate formulation [test] group).

As described in Section [5.1](#), eligible subjects will be admitted to the CRU on Day -1. At screening, subjects will be stratified and randomized as described in Section [5.1](#) and [Table RHCU.2](#). On Day 1, subjects will receive a single SC dose (Schedule of Activities, Section [2](#)) according to the randomization plan. The number of subjects in each weight category and assigned to each formulation is desired to be approximately equal. The number of subjects assigned to each site of injection location is desired to be balanced.

For purposes of this study, a subject completes the study when all scheduled procedures shown in the Schedule of Activities have been finished.

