10.3.2.2. Pharmacokinetic Statistical Inference

Pharmacokinetic parameters will be evaluated to determine the bioequivalence of ixekizumab alternate formulation (test) compared to the ixekizumab commercial formulation (reference). Log-transformed C_{max} and AUC parameters will be evaluated in a linear mixed-effects model

with fixed effects for formulation and a random effect for subject. The treatment differences will be back-transformed to present the ratios of geometric means and the corresponding 90% CI.

The t_{max} will be analyzed using a Wilcoxon rank sum test. Estimates of the median difference based on the observed medians, 90% CIs and p-values from the Wilcoxon rank sum test will be calculated.

Bioequivalence will be concluded if the 90% CI is completely contained within the interval (0.80, 1.25).

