3. INTRODUCTION

This SAP has been developed after review of the Clinical Study Protocol (final version dated 13 November 2019), Protocol Amendment (a) (final version dated 21 February 2020) and Protocol Amendment (b) (final version dated 29 September 2020).

This SAP describes the planned analysis of the safety, tolerability and pharmacokinetic (PK) data from this study. A detailed description of the planned TFLs to be presented in the clinical study report (CSR) is provided in the accompanying TFL shell document.

The intent of this document is to provide guidance for the statistical and PK analyses of data. In general, the analyses are based on information from the protocol, unless they have been modified by agreement with Eli Lilly and Company. A limited amount of information concerning this study (e.g. objectives, study design) is given to help the reader's interpretation. When the SAP and TFL shells are agreed upon and finalized, they will serve as the template for this study's CSR.

This SAP supersedes the statistical considerations identified in the protocol; where considerations are substantially different, they will be so identified. If additional analyses are required to supplement the planned analyses described in this SAP, they may be performed and will be identified in the CSR. Any substantial deviations from this SAP will be agreed upon with Eli Lilly and Company and identified in the CSR. Any minor deviations from the TFLs may not be documented in the CSR.

This SAP is written with consideration of the recommendations outlined in the International Conference on Harmonisation (ICH) E9 Guideline entitled Guidance for Industry: Statistical Principles for Clinical Trials¹ and the ICH E3 Guideline entitled Guidance for Industry: Structure and Content of Clinical Study Reports².

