5. STUDY DESIGN

Participants should follow local guidance and clinical research unit (CRU) precautions to minimize risk for Coronavirus Disease 2019 infection.

Study RHCU is a Phase 1, subject-blind, 2-arm, randomized, parallel-design study in healthy subjects.

All subjects will be screened within 28 days prior to enrollment. Eligible subjects will be admitted to the CRU on Day -1. At screening, subjects will be stratified into 1 of 3 weight categories (<70.0 kg, 70.0 to 80.0 kg, >80.0 kg). Within the 3 weight categories, subjects will be randomized 1:1 to either 80-mg ixekizumab commercial formulation (reference) or 80-mg ixekizumab alternate formulation (test) and subrandomized 1:1:1 to injection site (arm, thigh, or abdomen) (Table RHCU.1). On Day 1, subjects will receive a single SC dose according to the randomization plan (Table RHCU.1).

Table RHCU.1. Study RHCU Stratification and Randomization Plan

Weight Category (Subjects)	Formulation (80-mg ixekizumab)	Subcutaneous Injection Location ^a	Desired Number of Subjects
Low <70.0 kg (72 subjects)	Commercial (reference)	Arm	12
	Alternate (test)		12
	Commercial (reference)	Abdomen	12
	Alternate (test)		12
	Commercial (reference)	Thigh	12
	Alternate (test)		12
Medium 70.0 kg – 80.0 kg (72 subjects)	Commercial (reference)	Arm	12
	Alternate (test)		12
	Commercial (reference)	Abdomen	12
	Alternate (test)		12
	Commercial (reference)	Thigh	12
	Alternate (test)		12
High >80.0 kg (72 subjects)	Commercial (reference)	Arm	12
	Alternate (test)		12
	Commercial (reference)	Abdomen	12
	Alternate (test)		12
	Commercial (reference)	Thigh	12
	Alternate (test)		12

Abbreviations: RHCU = IIF-MC-RHCU; SC = subcutaneous.

^a A dose of investigational product will consist of 1 SC injection of 80-mg ixekizumab into the arm, thigh, or abdomen. All doses will be administered by trained site staff.

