7. SAMPLE SIZE JUSTIFICATION

Up to approximately 240 subjects may be enrolled so that approximately 216 subjects (108 in the 80-mg ixekizumab commercial formulation [reference] group and 108 in the 80-mg ixekizumab alternate formulation [test] group) complete the study.

A sample size of 108 subjects per treatment group will provide approximately 90% power that the 90% confidence interval (CI) of the geometric mean ratio of maximum observed drug concentration (C_{max}) and area under the concentration versus time curve (AUC) between groups will fall within equivalence range of 0.8 to 1.25. This sample size calculation was based on the assumptions that the PK parameters have log-normal distribution, the percent coefficients of variation (CV%) of C_{max} and AUC are less or equal to 48% (from study RHCT), the expected ratio of geometric means is between 0.997 to 1.04, and the CV% are the same for subjects from each treatment group.

Subjects who are randomized but not administered treatment and subjects who do not complete PK sampling (including Day 85) may be replaced so that approximately 216 subjects (108 for each treatment) complete the study.

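### The primary bioequivalence model omits the weight category and injection site used in randomisation, so its 90% CI is wider than the design requires if either affects exposure

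*SAP*

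**What the plan says.** SAP section 9.3.2 states that the log-transformed Cmax and both AUCs "will be evaluated in a linear mixed-effects model with fixed effects for formulation and a random effect for subject". The MODEL statement in its example SAS code lists formulation alone. Protocol section 10.3.2.2 has the same model, "with fixed effects for formulation and a random effect for subject", and so does the synopsis.

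The design has more structure than the model. Protocol sections 5.1 and 7.2 and SAP section 5 stratify subjects into three weight categories, randomise formulation 1:1 within each, and sub-randomise 1:1:1 to arm, thigh or abdomen. The target is 12 subjects per formulation in each weight-by-site cell. Protocol section 5.1 wants similar numbers in each weight category "to avoid a large difference in mean weight between the test and reference formulation groups". For site, protocol section 5.2 says only "The number of subjects assigned to each site of injection location is desired to be balanced".

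Elsewhere in the PK analysis the two factors are optional and descriptive: "PK parameters may be normalized by body weight for summarizing the data and may be summarized by site of injection location using descriptive statistics". The one planned sensitivity analysis changes which subjects are included, not the model. SAP section 11 reports no changes from the protocol analyses, and no reason is given for leaving the factors out.

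**The concern.** The 90% CI from this model decides bioequivalence for Cmax and both AUCs. Stratified, balanced assignment keeps between-stratum differences in exposure out of the formulation comparison. A model that ignores the strata still counts those differences as noise, so its standard error is larger than the true sampling variability of the estimate. The protocol's reason for stratifying by weight makes sense only if weight may affect exposure, so the issue follows from the plan's own rationale. For site, the documents show no effect and ask only for balance.

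What is at stake is efficiency: a wider interval than necessary, and a somewhat higher chance that a truly equivalent formulation fails. The direction is conservative.

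**Working it through.** **Inputs from the documents.** 108 per arm, CV up to 48%, limits 0.80 to 1.25, about 90% power, and "the expected ratio of geometric means is between 0.997 to 1.04" (SAP section 7). A 90% CI lying within the limits is equivalent to two one-sided tests at 5% each.

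**Assumed input.** R², the share of log-PK variance explained by weight category and site. The documents do not give it; 0 to 0.30 is shown.

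**The random subject effect does not help.** Each subject receives one dose and contributes one value per parameter, so this term cannot be separated from the residual. The planned model is in effect a two-sample comparison with 216 − 2 = 214 degrees of freedom.

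**Step 1: reproduce the plan's power.**
- Log-scale SD: σ = √ln(1 + 0.48²) = 0.4553.
- SE of the difference: 0.4553 × √(2/108) = 0.0620.
- Power of the two one-sided tests, integrated over the chi-square distribution of the variance estimate: 0.901 at ratio 1.04 and 0.948 at ratio 0.997.

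The stated figure reproduces, and 108 is the smallest number per arm that reaches 90% at ratio 1.04.

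**Step 2: compare the two models.** Take 48% as the total CV and the cells as balanced. The formulation estimate is then the same under both models, and its true SD is σ√(1 − R²) × √(2/108).
- Planned model: estimates σ, with 214 degrees of freedom.
- Adjusted model: estimates σ√(1 − R²), with 214 − 2 (weight) − 2 (site) = 210 degrees of freedom.
- Coverage of the planned interval: approximately 2Φ(t/√(1 − R²)) − 1, where t is the 95th percentile of t with 214 degrees of freedom.

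Results at CV 48%. Power is at ratio 1.04; type I error is one-sided, per parameter, at a true ratio of 1.25.

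| R² | Power, planned | Power, adjusted | Log half-width, planned | Log half-width, adjusted | Coverage, planned | Type I error, planned |
|---|---|---|---|---|---|---|
| 0 | 0.901 | 0.901 | 0.102 | 0.102 | 90% | 5.0% |
| 0.10 | 0.914 | 0.927 | 0.102 | 0.097 | 92% | 4.2% |
| 0.20 | 0.927 | 0.951 | 0.102 | 0.092 | 94% | 3.3% |
| 0.30 | 0.940 | 0.970 | 0.102 | 0.086 | 95% | 2.5% |

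The adjusted model's type I error stays at 5.0%. At R² = 0.05, power is 0.907 vs 0.914.

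**Step 3: other design points**, for R² = 0.10, 0.20 and 0.30.
- Ratio 0.997, CV 48%: 0.959 vs 0.967; 0.970 vs 0.982; 0.980 vs 0.992.
- Ratio 1.04, CV 40% (assumed): 0.974 vs 0.979; 0.981 vs 0.988; 0.986 vs 0.994.

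Across these cases the gain is about 0.5 to 3 percentage points.

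**Step 4: simulation.** There were 20,000 runs per case, with the explained variance put on weight category only.
- Balanced cells, ratio 1.04: 0.912 vs 0.926; 0.928 vs 0.952; 0.941 vs 0.971, in agreement with the table.
- Unbalanced cells (240 assigned as 13 or 14 per cell, 24 lost at random): power 0.902 vs 0.901 at R² = 0, then 0.913 vs 0.928; 0.927 vs 0.952; 0.939 vs 0.970. Planned type I error is 4.4, 3.5 and 2.7%; adjusted is 5.2, 4.9 and 4.9%.

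**Step 5: if 48% is a within-category CV.** The documents say only that it comes from study RHCT. On this reading the total SD is larger, and simulated planned power at ratio 1.04 is 0.883, 0.858 and 0.827 at R² = 0.10, 0.20 and 0.30. The adjusted model stays at about 0.90.

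**The case against.** The strongest reply is that nothing is broken. The planned analysis is conservative, is stated identically in both documents, and reaches its power target on its own inputs. Its power even rises with R², because the stratification is doing its work. Balancing mean weight between groups, the stated purpose, is achieved without a covariate. The benefit depends on an R² that the documents do not give, and at R² = 0 there is none. No site effect is shown. Both documents also leave room for additional analyses.

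Much of this stands. The point concerns efficiency, not validity; its size is conditional; and the case for site is weaker than the case for weight. Three parts do not carry through. Meeting the power target depends on 48% being the total CV, and the other reading makes the loss larger. Room for extra analyses is not pre-specification and does not change the interval that decides the result. And the lack of a known R² does not favour the planned model, since adjustment costs nothing measurable when R² is zero.

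**Conclusion.** The concern holds. The deciding model omits the factor within which formulation is randomised, and the sub-randomised site factor as well. If either explains exposure variance, the 90% CI over-covers and modest power is forgone: about 1.3, 2.4 and 3.0 points at R² = 0.10, 0.20 and 0.30 with CV 48% and ratio 1.04, and less at ratio 0.997 or at CV 40%. These figures assume log-normal data, equal variances, 48% as the total CV and near-balanced cells; moderate random imbalance barely changes them. The planned model does not raise the risk of a false bioequivalence conclusion and does not systematically bias the ratio. The omission and its direction are certain; its size in this trial is not, because R² is unknown.

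**What to change.** In SAP section 9.3.2, make the primary model log(parameter) = formulation + weight category + injection site, all as fixed effects and with categories as randomised. Judge the adjusted geometric mean ratio and its 90% CI against 0.80 to 1.25. Keep the formulation-only model as a sensitivity analysis, and run the complete-sampling sensitivity analysis with the adjusted model too. If site is judged irrelevant, weight category alone is the minimum that the protocol's rationale supports; settle on one primary model in advance. Update the CLASS and MODEL statements. The ESTIMATE statement needs editing in any case, because it names a treatment variable that appears in neither. Whether the random subject term stays makes no difference to this point.

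SAP section 3 says: "This SAP supersedes the statistical considerations identified in the protocol; where considerations are substantially different, they will be so identified". So replace the no-changes statement in SAP section 11 with an entry for this change, and align protocol section 10.3.2.2 and the synopsis. Finalise this before any treatment comparison is seen.

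No new data are needed, since both factors are fixed at randomisation. The statistical cost is 4 of 214 residual degrees of freedom: at R² = 0, power is 0.9005 instead of 0.9006. The real cost is the documentation of a changed primary model.

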Pharmacokinetic parameters will be evaluated to determine the bioequivalence of ixekizumab alternate formulation (test) compared to the ixekizumab commercial formulation (reference). Log-transformed maximum observed drug concentration (C_{max}) and area under the concentration versus time curve (AUC) parameters will be evaluated in a linear mixed-effects model with fixed effects for formulation and a random effect for subject. The treatment differences will be back-transformed to present the ratios of geometric means and the corresponding 90% confidence interval (CI). Bioequivalence will be concluded if the 90% CI is completely contained within the interval (0.80, 1.25).

The time to maximum drug concentration (t_{max}) will be analyzed using a Wilcoxon rank sum test. Estimates of the median difference based on the observed medians, 90% CIs, and p-values from the Wilcoxon rank sum test will be calculated.

Safety laboratory parameters and vital signs data will be listed and summarized using standard descriptive statistics, where possible. Suicidal ideation and/or behavior and self-injurious behavior with no suicidal intent, based on the C-SSRS, will be listed by subject. Only subjects that show suicidal ideation/behavior or self-injurious behavior without suicidal intent will be included in the listing (i.e., if a subject's answers are all 'no' for the C-SSRS, then that subject will not be displayed). Hospital Anxiety Depression Scale (HADS) item scores will be listed for subjects with HADS depression subscale ≥ 11 at any time.

The frequency and percentage of subjects with preexisting antidrug antibodies (ADAs) and with treatment-emergent ADAs (TE-ADAs) to ixekizumab will be tabulated. Treatment-emergent ADAs are defined as those with a titer 2-fold (1 dilution) greater than the minimum required dilution if no ADAs were detected at baseline (treatment-induced ADAs) or those with a 4-fold (2 dilutions) increase in titer compared to baseline if ADAs were detected at baseline (treatment-boosted ADAs). For the TE-ADA subjects, the distribution of maximum titers will be described. The frequency of neutralizing antibodies will also be tabulated in TE-ADA subjects.

Additional analysis may be performed, if warranted, upon review of the data.

2. Schedule of Activities

Study Schedule Protocol I1F-MC-RHCU

Procedure	Screening -28 to -2 days prior to Day 1	Days																	Comments

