5.4. Scientific Rationale for Study Design

Conducting the study in healthy subjects mitigates the potential confounding effects of the disease state and concomitant medications in patients. A population of healthy subjects is frequently used in the assessment of the bioequivalence of both small and large molecules.

Single doses of ixekizumab and the PK sampling time points have been selected to generate PK profiles sufficient to fulfill the study objectives.

A parallel-group design is chosen because a crossover design is impractical for ixekizumab, which has a half-life of approximately 13 days. Additionally, a crossover study could confound PK data if subjects develop neutralizing antidrug antibodies (ADAs).

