6. TREATMENTS

The following is a list of the study treatment abbreviations that will be used in the TFLs.

Study Treatment Name	Abbreviation	Treatment order in TFL
80-mg ixekizumab commercial formulation	Reference	1

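### Do the redundant random subject effect and the misnamed contrast term in the SAP's example code put the bioequivalence analysis at risk?

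*SAP*

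**What the plan says.** The synopsis of the protocol specifies a "linear mixed-effects model with fixed effects for formulation and a random effect for subject", and protocol section 10.3.2.2 repeats the model "with fixed effects for formulation and a random effect for subject". SAP section 9.3.2 uses the same model for log Cmax, AUC(0-∞) and AUC(0-tlast). The formulation difference is back-transformed to a ratio of geometric means with a 90% confidence interval, and bioequivalence requires that interval to lie within (0.80, 1.25).

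A block headed as example SAS code follows. It runs separately by parameter. Its CLASS statement is "class formulation subject", its MODEL statement has `formulation` as the only effect, its RANDOM statement is "random intercept / subject=subject", and its contrast is "estimate 'Test - Ref' trtmnt -1 1 / cl alpha=0.1".

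On the design, protocol section 5.4 says "A parallel-group design is chosen because a crossover design is impractical for ixekizumab", and SAP section 5 gives each subject a single dose. SAP section 9.1 names SAS version 9.4 or later as the software. SAP section 3 says "This SAP supersedes the statistical considerations identified in the protocol", and SAP section 11 records no changes from the protocol analyses.

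**The concern.** A random subject effect belongs to a crossover or other repeated-measures design. Here each fit has one record per subject, so the subject intercept and the residual describe the same variation. The data cannot tell the two variances apart, and a fitting routine may issue singularity or Hessian warnings. If a routine handled this badly, the standard error could be wrong, and with it the width of the interval that decides bioequivalence.

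The contrast raises a separate worry. `trtmnt` appears in neither CLASS nor MODEL, so the one statement meant to return the Test minus Reference difference and its limits refers to nothing in the model.

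This is the only model specified for the primary objective. The sensitivity analysis in the same section changes which subjects are included, not the model, so it inherits both features.

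**Working it through.** **Inputs.** SAP section 7 (same text in protocol section 10.1): 108 subjects per group, CV up to 48%, true ratio between 0.997 and 1.04, log-normal data, equal CV in both groups. SAP section 9.3.2: 90% interval, limits 0.80 and 1.25.

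**1. The plan's own power figure.**
- Log-scale SD = sqrt(ln(1 + 0.48²)) = sqrt(0.2073) = 0.4553.
- SE of the log difference = 0.4553 × sqrt(2/108) = 0.0620.
- Normal approximation at ratio 1.04, with ln 1.25 = 0.2231 and ln 1.04 = 0.0392: Φ((0.2231 − 0.0392)/0.0620 − 1.645) + Φ((0.2231 + 0.0392)/0.0620 − 1.645) − 1 = 90.2%.
- Exact calculation with the t distribution on 214 df, integrated over the distribution of the estimated variance: 90.1% at 1.04 and 94.8% at 0.997. The smallest group size giving 90% at 1.04 is 108.

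The stated figure of approximately 90% is reproduced by a two-group calculation with a single variance, so the sample size never relied on separating subject from residual variance.

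**2. What the random effect does.** Write the subject variance as a and the residual variance as b. With one record per subject, the covariance matrix of the data is (a + b) × I, so the likelihood depends only on a + b. In one simulated data set (108 + 108 subjects, CV 48%, true ratio 1.04), the estimated total variance was divided in four ways:

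| Share given to subject | REML log-likelihood | Log difference | SE |
|---|---|---|---|
| 0% | 70.1633 | 0.0375 | 0.0582 |
| 25% | 70.1633 | 0.0375 | 0.0582 |
| 50% | 70.1633 | 0.0375 | 0.0582 |
| 90% | 70.1633 | 0.0375 | 0.0582 |

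The ordinary two-group linear model gives the same estimate and SE. The 90% interval is exp(0.0375 ± 1.652 × 0.0582) = 0.943 to 1.143.

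**3. Degrees of freedom.** Every cell of the 2 × 2 information matrix for (a, b) equals 214/(2σ⁴), with σ² = a + b, so its rank is 1. The variance of the contrast is v = (2/108)σ², and the estimate of σ² has variance 2σ⁴/214. A Satterthwaite-type df, to which the Kenward-Roger option reduces here, is 2v²/var(v) = 2 × (2/108)²σ⁴ ÷ [(2/108)² × 2σ⁴/214] = 214. Two different generalized inverses of the singular matrix both returned 214.

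**4. The contrast name.** CLASS lists `formulation` and `subject`. MODEL contains `formulation` alone, which has two levels. A contrast with coefficients −1 and 1, labelled as Test minus Reference, can refer only to that effect.

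**5. Order of levels.** Coefficients −1 1 give Test minus Reference if Reference sorts first. SAP section 6 lists Reference as number 1 under "Treatment order in TFL". That is an order for displays; it suggests the coding but does not fix it. If the levels sorted the other way, the simulated interval would become 1/1.143 to 1/0.943 = 0.875 to 1.060. Because 0.80 = 1/1.25, an interval lies inside the limits exactly when its reciprocal does, so the decision would be the same. The printed ratio would be inverted, which a comparison with the two geometric means in the summary tables would show.

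**The case for a change.** The best argument for acting is that a prespecified primary analysis should run as written, and this code does not. The redundancy is also in the governing prose of both documents, so calling the code an example does not excuse it. A programmer who renames the term or drops the random effect would depart from the signed text without a record. In addition, one non-SAS mixed-model routine, fitted to another simulated data set of the same design, warned of a non-positive-definite Hessian and printed an SE of 0.0343 where the correct value was 0.0653. An interval built on that would be about half its proper width (0.0343/0.0653 = 0.53).

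The facts about the code and the model stand. The consequences do not follow:
- The SE of 0.0343 comes from software that the plan does not use, since SAP section 9.1 prescribes SAS. No wrong result under SAS has been shown. SAS was not run here, so a warning in the log remains possible.
- An effect missing from the model returns no contrast, so the slip cannot pass unnoticed into a wrong ratio.
- Correcting a variable name in illustrative code does not depart from the analysis that the prose prescribes. SAP section 11 is accurate on this point, because the protocol and the SAP specify the same model.

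**Conclusion.** No change to the plan follows. The contrast name is a clerical slip in illustrative code. It leaves the analyst no freedom, because the text fixes the parameters, the log scale, the direction of comparison, the 90% interval and the limits, and only one effect can be meant. Rewriting the model without the random effect would be tidier but would gain nothing: the ratio, SE, df (214), interval, power (90.1% at 1.04, 94.8% at 0.997) and decision are the same with or without it.

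This rests on one value per subject per parameter in each fit, which the single-dose parallel design and the by-parameter run ensure, and on a fit in the named software that returns the correct total variance. The second condition is supported by the algebra and the generalized-inverse check, not by a SAS run. Whether body weight or injection site should enter the model is a separate question that this point does not settle.
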